9.2.1 Treatment Assignment Procedures

A randomized, double-blind, placebo-controlled trial design (CE cream versus placebo) will be used in this study. SAS V9.3 will be used by the study biostatistician to generate the stratified, randomization lists. Patients will be stratified by site, hysterectomy status, and duration since menopause (<10 and ≥10 years). The randomization lists will be distributed to each site’s research pharmacy (or their designee). Those conducting the primary and secondary measurements as well as the patients will be blinded to treatment assignment. These data will *not* be housed in study’s database (i.e. REDcap®).

At the discretion of the primary investigators at any of the clinical sites, they may request the primary site PI to have the blind broken. The primary site PI—likely in consultation

with the Safety Monitor, as needed—will then request this information of the DCC study database manager (permitting [name] to remain blinded) if it is clinically needed to understand the medication that the patient is receiving. It is anticipated that this would only be requested for important medical reasons, e.g., a serious adverse event or significant allergic reaction to study cream. In most cases, patient skin irritation with cream application could prompt discontinuation of the study medication without unmasking. There is no plan for clinical site research pharmacists to unmask participants, research coordinators, or local site PIs directly. Planned breaking of the randomization codes will only be after all participants have reached the primary study outcome time point one year postoperatively; there are no plans for interim/ early data analyses.

9.3 Interim analyses and Stopping Rules

No analyses of efficacy are planned to be presented until the end of the trial. Additional DSMB review may be requested by the UTSW PI and biostatistician, and an emergency review by the DSMB requested at any time if questions of participant safety arise. Between-groups comparisons of safety variables will be presented to the DSMB.

Should the DSMB decide to issue a recommendation to terminate or alter the study protocol based on safety, futility, or poor study performance (e.g., slow accrual, high loss-to-follow-up, poor quality control) a full vote of the 3 site PI's will be required. Examples of findings that might trigger a safety review are the number of SAEs overall, the number of occurrences of a particular type of SAE, severe AEs/reactions, or increased frequency of events. Such findings are presented to the study biostatistician or to the Data and Safety Monitoring Board (DSMB) statistician to review the events by group to determine whether there are statistical as well as clinical concerns. The statistician reports the findings to a closed session of the DSMB or to the Safety Officer and/or NIA. The findings are used to determine what steps will be taken.

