7.4 Reporting Procedures

Each clinical investigator is responsible for reporting serious or unexpected adverse events to the IRB at their institution and to the Safety Monitor. The Safety Monitor/Officer (currently DSMB Chair, [name]), DCC Biostatistician (currently [name]), and NIA Project Scientist or Program Officer are notified by email when a report of any serious adverse event is entered into the REDCap database. The Safety Monitor summarizes the case; if it is potentially related to the intervention, the Safety Monitor reports it to the NIA Program Officer and the remaining DSMB members in an expedited manner (i.e., within 24 hours of learning of these events). The Safety Monitor (currently [name]) will determine whether the case should be reported to the IRBs at all the institutions participating in the trial. The DCC summarizes all SAE’s, including those that are definitely not related to the intervention, for the DSMB at each DSMB meeting.

Approximately every 6 months, or more frequently upon request of the Chair of the DSMB, the DCC will summarize all adverse events (including serious, unexpected and expected) by randomization group in a report to the DSMB. In addition, the report will contain accrual and drop-out rates. The DSMB will summarize their findings to the NIA with approval to continue the clinical trial, or a recommendation to modify the trial or terminate the trial.

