7.6 Safety Monitoring

The NIA has appointed a Data Safety Monitoring Board (DSMB), which will regularly evaluate the safety of the participants in IMPROVE. The IMPROVE UTSW PI and Biostatistician will be blinded to treatment allocation using dummy treatment group assignments while the DSMB and statistician/ programmer will be unblinded. The DSMB will consist of a chairperson and 2 other individuals who have expertise in clinical study design/ conduct and biostatistics. All board members will be independent of the institutions and investigators participating in the trial and have no financial ties to Pfizer (maker of Premarin® vaginal cream) or to the outcome of the trial.

The DSMB will review the study design and plans for recruitment, adherence, interventions, data quality and safety monitoring. The responsibilities of the DSMB are to:

- evaluate the safety of trial participants
- ensure confidentiality of data and the results of monitoring
- report to the UTSW PI and biostatistician on the safety of participants
- make recommendations on continuation, termination, or modifications to the trial

DSMB Process: There will be 2 sections of the DSMB meeting: open and closed. In the open section of the meeting, the PI and Biostatistician will present the report to the DSMB and answer questions. The closed section of the meeting will include the members of the DSMB only.

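### Section 9.3 puts an undefined vote of the three site PIs on DSMB recommendations to stop or alter the trial, safety included, and this is not reconciled with Sections 7.4 and 7.6

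*Combined protocol and SAP*

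**What the plan says.** Section 9.3 (Interim analyses and Stopping Rules) sets the trigger: "Should the DSMB decide to issue a recommendation to terminate or alter the study protocol based on safety, futility, or poor study performance". In that event it requires "a full vote of the 3 site" PIs. Slow accrual, high loss to follow-up and poor quality control are given as examples of poor performance. Safety has no separate treatment.

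Section 7.6 (Safety Monitoring) says that the NIA appoints the board. On membership it states: "All board members will be independent of the institutions and investigators participating in the trial". One of the board's duties is to "make recommendations on continuation, termination, or modifications to the trial". After each review the board writes to the UTSW PI and biostatistician with its recommendation. On access to the discussion: "The closed section of the meeting will include the members of the DSMB only".

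Section 7.4 (Reporting Procedures) has the board report its findings to the NIA, either approving continuation or making "a recommendation to modify the trial or terminate the trial".

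Neither 7.4 nor 7.6 mentions a vote by investigators.

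**The concern.** The protocol describes one process in three places, and only one of them contains the vote. Someone following 7.4 and 7.6 would send a stop-for-safety recommendation straight to the NIA and the UTSW PI. Someone following 9.3 could reasonably hold it until three investigators had voted, and 9.3 sets no deadline.

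There is also a question of what the voters would know. Between-group safety comparisons go to the DSMB, and a safety recommendation may well rest on them. The blinding plan keeps actual treatment assignment from the investigators. They would therefore vote without the evidence behind the recommendation, unless someone departed from the blinding plan to show it to them. At stake are the speed of action on a safety signal and the integrity of the blind during follow-up. Both matter most when there is least time to settle how 9.3 should be read.

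**Working it through.** No arithmetic applies. The point rests on no sample size, event count or error rate, so the check is a comparison of sections.

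**Step 1: what 9.3 fixes and what it leaves open.** It fixes the trigger (the board decides to issue a recommendation to terminate or alter), the grounds (safety, futility, poor performance) and the voters (the three site PIs). It leaves open:
- whether the vote is on issuing, accepting or implementing the recommendation
- the majority needed
- the time allowed
- the consequence of a vote against.

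**Step 2: place the vote in the reporting chain.**

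| Section | Step | Vote mentioned? |
|---|---|---|
| 7.6 | Board makes recommendations | No |
| 7.6 | Letter to UTSW PI and biostatistician after each review | No |
| 7.4 | Findings and recommendation to the NIA | No |
| 9.3 | Board decides to issue a recommendation | Yes |
| 11.4 | NIA, IRB, OHRP, FDA or other agencies may discontinue at any time | No |

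**Step 3: test the two readings.**
- *The vote comes before issue.* The 9.3 trigger is a decision to issue, so this is a natural reading. It makes issue depend on the investigators, whereas 7.4 and 7.6 have the board report unconditionally. The sections then conflict directly.
- *The vote is on acceptance or implementation.* The recommendation goes out as in 7.4 and 7.6, and the PIs then decide how to act on it. The sections can coexist, but nothing in 9.3 says this is meant.

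**Step 4: add the blinding provisions.** Section 7.6 keeps the UTSW PI blinded through dummy group labels, limits closed sessions to board members, and restricts the real codes at UTSW to the unblinded statistician/programmer. Section 9.2.1 has no plan for pharmacists to unmask local site PIs directly, and places planned code-breaking after all participants reach one year. Section 10.1 describes clinic providers and surgeons as blinded. The UTSW PI does present the dummy-coded report in open session, so that voter sees some grouped safety data. The documents do not say that the other two PIs see even this, and no provision gives any of the three the actual assignments for a vote. The problem exists on either reading in Step 3.

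**Step 5: compare timing.** Section 7.4 sets 24 hours for a potentially related SAE to reach the NIA Program Officer and the remaining board members. The vote in 9.3 has no time limit.

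**The case against.** The strongest reply is that 9.3 describes how investigators adopt advice. The independence stated in 7.6 concerns who sits on the board. The board is advisory throughout, so a vote by those who must carry out its advice does not negate independent membership. Section 13 gives the Steering Committee, which includes the site PIs, the main role in revising the protocol, and this fits the implementation reading. Safety information also reaches the NIA without any vote: 7.4 notifies an NIA officer of every SAE entered, 9.3 itself allows findings to go to the Safety Officer and/or the NIA, and 11.4 lets the NIA and others stop the study at any time.

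Much of this stands. A reader might infer that 9.3 contradicts the board's independence, or lets the site PIs veto the NIA. The documents do not support either: the stated independence is about membership, 9.3 does not say the vote blocks transmission, and 11.4 leaves the NIA's power intact. A reader might also infer that the PIs must either be unblinded or be able to hold up a recommendation. That does not follow, because they could vote blinded with no power to stop the recommendation reaching the NIA.

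The reply does not show that the implementation reading is the one written. It also does not explain why safety falls under a vote whose effect is undefined. The other routes carry SAE reports and safety findings, but none of them guarantees that the board's recommendation arrives without waiting for the vote.

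**Conclusion.** The point holds as an unreconciled governance rule, and it should be corrected. It is certain from the text that 9.3 requires the vote, that safety is not exempted, and that 7.4 and 7.6 contain no such step. Which reading was intended is uncertain. The conflict is direct if the vote comes before issue, and a tension if the vote concerns only acceptance or implementation. On both readings, investigators without access to data by actual treatment may be voting on a safety recommendation that rests on such data.

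The size cannot be given as a power, error or delay figure, because the documents supply no input for one. The existing SAE reporting and the agencies' power to discontinue reduce the likely harm. The concern about the evidence base assumes a recommendation based on by-arm comparisons. It would not apply to one based on, for example, accrual.

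**What to change.** Reconcile 9.3 with 7.4 and 7.6 by stating in 9.3 that:
- DSMB recommendations go to the NIA as 7.4 already provides
- recommendations made on safety grounds are not conditional on a site-PI vote
- site PIs receive no by-arm data for the purpose of any vote.

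The vote may be kept for recommendations about accrual or study performance, and for the investigators' implementation of protocol changes. Where it is kept, 9.3 should say what is being decided, by what majority, by when, and what follows a vote against.

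The cost is a few sentences, with no change to sample size, analysis or study procedures. The downside is small: investigators have less say over safety-based recommendations.

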9.4 Outcomes

9.4.1 Primary outcome

Aim 1. The primary outcome is dichotomous success/failure of prolapse repair (see Item 9.1 above) as measured 12 months postoperatively. This is a composite outcome with failure defined by objective prolapse beyond the hymen, subjective sense of bulge by the patient, or retreatment by any intervention. It is not anticipated that any component of this primary outcome will require adjudication by committee.

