Design: Randomized, double-blind, placebo-controlled trial of pre- and postoperative intravaginal estrogen therapy in 222 postmenopausal women with symptomatic prolapse undergoing a standardized surgical repair using native tissue.

Primary outcome: prolapse recurrence as defined by a composite of objective prolapse beyond the hymen, subjective/symptomatic prolapse (feeling of a bulge or *no change* or *worse* on the patient's global impression of improvement), or retreatment (e.g., reoperation or pessary use) assessed 1 year postoperatively. *Time to failure* will be compared in the two groups.

Important secondary outcomes assessing for changes in overactive bladder and urinary incontinence symptoms will be made by comparing symptoms (validated questionnaires) from Baseline to Pre-op/time of surgery. Aim 3 (see above, histomorphology, connective tissue studies) will be assessed from full thickness anterior apical vaginal wall biopsies taken at the time of surgery.

Interventions and Duration

Intervention: 1g conjugated estrogen (CE) cream (Premarin®, Pfizer Inc.) given nightly for 2 weeks then twice-weekly to complete planned 6-8 weeks (5 weeks minimum) therapy before a standardized uterosacral or sacrospinous ligament suspension transvaginal prolapse repair surgery. Those with a uterus will undergo concomitant total vaginal hysterectomy first. Twice-weekly CE cream application is then resumed upon discharge and continued for 1 year postoperatively.

Comparator: placebo vaginal cream, same schedule

Duration: The primary outcome of prolapse recurrence is assessed at one year postoperatively with continued surveillance of participants until 3 years postoperatively.

Sample Size and Population

Total sample size: N=222; 111 per treatment group

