9 STATISTICAL CONSIDERATIONS

9.1 General Design Issues

A large simple trial (randomized, controlled) design was selected to evaluate for possible superiority of vaginal estrogen cream use compared to placebo. The primary outcome is a comparison by treatment group of time-to-failure of the prolapse repair at 1 year after surgery with "failure" defined by the *any* of these outcomes occurring:

- Recurrent prolapse beyond the hymen of the anterior or posterior vaginal wall *or* apical descent >1/3 into the vaginal canal based on continuous measurements of the Pelvic Organ Prolapse Quantification (POP-Q)⁷¹ examination
- Report of any symptoms of bulge: “yes” to question #3 of the Pelvic Floor Distress Inventory, “Do you usually feel a bulge or something falling out that you can see or feel in your vaginal area?” or *no change* or worse on the Patient Global Impression of Improvement (PGI-I).
- Retreatment of prolapse with either pessary or surgery

The null hypothesis for this study is that 12 months following transvaginal native tissue repair for prolapse with or without preoperative and continued postoperative local estrogen treatment, women will have the same rate of recurrent prolapse. The current definition of success in a surgical trial used by NICHD’s Pelvic Floor Disorders Network (PFDN) is this same composite of no prolapse beyond the hymen, no symptomatic recurrence, and no retreatment.^{81,82}

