9.2 Sample Size and Randomization

The literature reports failure by the above definition occurring in ~40% of patients with a native tissue USLS (i.e., ~60% “success”).⁶⁹ A 2-sided logrank test with an overall sample size of **188 subjects** (94 each group) achieves 80% power at a 0.05 significance level to detect a hazard ratio of 0.5188 when the proportion of those "surviving" (i.e. "successes") in the control group is **65% compared to 80%** in the treated group, **measured at 1 year**. This presumes the accrual pattern across the study time period (3 years of accrual) is uniform. This N=188 already accounts for **25%** either lost to follow-up *or non-adherent to study cream* in the control and treatment groups. Allowing for an additional **15% loss of participants** from baseline to surgery, **222 total participants** are needed.

Potential problems & alternatives:

Differences in baseline characteristics between the groups may occur by chance, but we will mitigate that risk by stratifying by clinical site, hysterectomy status, and duration since menopause (<10y & ≥10y).

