9.5 Data Analyses

Aim 1. The **primary outcome** will be analyzed according to the assigned treatment group (modified intention-to-treat): i.e., all participants that are randomized *and* undergo a surgical prolapse repair *and* have at least one postoperative assessment will be analyzed according to their randomized assignment group. All eligible subjects who consent to the study and are enrolled will be available for analysis of baseline characteristics, and those that are randomized and use their study drug will be monitored for adverse events, but they must meet the additional qualifications above (i.e., undergo surgery and have a postoperative assessment) to be analyzed for the primary study outcome. At baseline, continuous measures will be compared between groups with Student's t-test and chi-square (or Fisher's exact test) for categorical measures. Scores from repeated surveys are continuous outcomes data and will be analyzed using repeated measures analysis of variance. We will test for interactions between time effect and treatment effect. For categorical data (e.g. prolapse stage), the analysis will be by categorical data modeling using weighted least squares and mixed logit models, with cross-sectional assessments (at specific time intervals) by chi-square. For missing follow-up points there are two possible approaches: (i) if there are few missing follow-up points, then their values may be imputed through multiple imputation methods, in which case repeated measures analysis of variance may be used following multiple imputation; (ii) more likely, we will make time a random effect and a mixed effects model with repeated measures will be applied. Time-to-event or event-free-time will be analyzed using survival methods to include the log-rank test and Cox regression. For measures that may not be assumed normal, the data will be transformed using a rank transformation prior to analysis.

In accordance with NIH policy, we will include an analysis of the intervention effect (CE cream) performed by racial/ethnic subgroups, recognizing that the analyses will not have high statistical power for detecting clinically meaningful differences between races/ethnicities.

Aim 2 Outcomes. As above, continuous scores from repeated surveys will be analyzed using repeated measures analysis of variance with appropriate corrections made, as necessary, for missing data.

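### The primary outcome is time to failure in Section 9.1 but a dichotomous 12-month status in Section 9.4.1, Section 9.5 names no primary test, and the stated 80% power fits neither if follow-up stops at 12 months

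*Combined protocol and SAP*

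**What the plan says.** **Section 9.1:** "The primary outcome is a comparison by treatment group of time-to-failure of the prolapse repair at 1 year after surgery", with failure met if any component occurs (descent on POP-Q, bulge or an unfavourable PGI-I, retreatment). The null hypothesis in the same section concerns the position 12 months after surgery: "women will have the same rate of recurrent prolapse".

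**Précis:** describes a composite assessed at one year, then says that time to failure will be compared between groups.

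**Section 9.2:** "A 2-sided logrank test with an overall sample size of 188 subjects (94 each group) achieves 80% power at a 0.05 significance level". The inputs are 65% v 80% success at one year, a hazard ratio of 0.5188, three years of uniform accrual, and 25% lost or non-adherent already allowed for.

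**Section 9.4.1:** "The primary outcome is dichotomous success/failure of prolapse repair", with a reference back to Section 9.1 and measurement at 12 months after surgery.

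**Section 9.5:** defines the modified intention-to-treat population for the primary outcome but labels no test as primary. It offers chi-square at specific times for categorical data and, for time-to-event data, "survival methods to include the log-rank test and Cox regression".

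**Section 6 (Table 1 and visit descriptions):** components are assessed before 12 months. POP-Q is done at 1 and 6 months, the bulge question and PGI-I at 6 months, and bulge and retreatment are asked in the 3- and 9-month calls.

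**The concern.** Time to first failure and status at 12 months are different endpoints when a component can come and go. Bulge and PGI-I describe how a woman feels when asked, and Section 2.1 itself reports remissions of grade 2–3 cystocele and rectocele in an observational cohort. The two endpoints also treat dropout differently. A woman lost after a clean 6-month visit contributes censored time to a log-rank test but has no 12-month status.

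This is the trial's single confirmatory comparison. If the text supports two versions, the choice can be made after the data are seen, and a result that is significant on one version only has no pre-stated interpretation. Aim 3 inherits the problem, because it divides women into repair failures and successes. The sample size also depends on which version is meant and on when follow-up is cut off.

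**Working it through.** **1. Same woman, two sections**

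| Course | 9.1, time to failure | 9.4.1, literal 12-month status |
|---|---|---|
| Bulge at 3, 6 or 9 months, absent at 12 | Failure | Success |
| Clean at 6 months, then lost | Censored | No status |
| Retreated at 5 months | Failure | Failure, if retreatment is counted cumulatively |
| First failure at 12 months | Failure | Failure |

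The endpoints part company for some women, not all.

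**2. Reproducing the 188 in Section 9.2**

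- Hazard ratio from the stated proportions: ln 0.80 / ln 0.65 = 0.518, in line with 0.5188.
- Events (Schoenfeld, two-sided 0.05, 80% power): 4 × (1.960 + 0.842)² / (ln 0.5188)² = 73.
- Assumptions not in the documents: exponential hazards (0.431 and 0.223 per year, from 65% and 80%), and the 25% modelled as exponential loss (0.288 per year).
- Probability of an observed event by time t: λ/(λ+η) × [1 − exp(−(λ+η)t)].
- With uniform 3-year accrual and a common close one year after the last entry, follow-up runs from 1 to 4 years and the average event probability is 0.391. Then 73 / 0.391 gives N = 187, and 188 women give 73.5 events and 80.3% power. This reproduces the plan.
- Capping each woman at the 3-year visit gives N = 190 and 79.7% power.
- 188 / 0.85 = 221.2, rounded up to 222, which also reproduces.

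**3. The same 188 women with follow-up stopped at 12 months**

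Power = Φ(√events × |ln 0.5188| / 2 − 1.960).

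| Analysis | Event probability | Events | Power |
|---|---|---|---|
| Log-rank to 12 months, no loss | (0.35 + 0.20)/2 = 0.275 | 51.7 | 65.5% |
| Log-rank to 12 months, 25% loss | 0.241 | 45.3 | 59.8% |
| Log-rank, 1 to 4 years, 25% loss | 0.391 | 73.5 | 80.3% |

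For 80% power, a log-rank test stopped at 12 months needs 73 / 0.275 = 266 women without loss, or 303 with it. A comparison of two proportions, 65% v 80%, needs 138 per arm (276 evaluable). With 94 per arm it has 63.6% power, and with about 70 per arm about 51%.

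**4. What a free choice of test would cost**

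Simulated trials with 94 per arm, 35% v 20% failure and contacts at 1, 3, 6, 9 and 12 months, comparing log-rank with chi-square:

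- *Irreversible failure.* The tests disagree on significance in about 3% of trials without loss and 5–6% with 25% loss. Under the null, each test alone rejects in about 5%, and taking whichever is significant rejects in about 5.5–7%. Individual runs of 3,000 to 10,000 trials vary by a few tenths of a point.
- *Reversible failure, no loss.* The share of early failures that resolve is assumed, since the documents give no rate.

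| Early failures resolving | Disagreement | Chi-square power | Either-test type I error |
|---|---|---|---|
| 10% | 12% | 58% | 6.2% |
| 25% | 20% | 50% | 7.6% |
| 50% | 35% | 37% | 8.8% |

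Log-rank power stays at about 64% throughout. The simulation treats all five contacts as equal assessments. In the plan the 1-month visit has POP-Q but no symptom questionnaire, and the 3- and 9-month calls cover only bulge and retreatment.

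**The case against.** The strongest reply is that there is no real conflict. Section 9.4.1 refers to 9.1, where failure means any component occurring, so the dichotomous outcome may be just the event indicator: failed by 12 months, yes or no. On that reading a bulge at 3 months counts under both sections. The log-rank test is also much the better supported. The précis and 9.1 speak of time to failure, 9.2 sizes the trial on the log-rank, and no section ties chi-square to the composite. In 9.5 the example given for categorical methods is prolapse stage. Finally, 9.5 admits every woman with surgery and one postoperative assessment, so a woman lost after 6 months is in the primary population, which suits a time-to-event analysis.

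Much of this stands. A reader might infer that the two sections necessarily classify women differently, or that two equally supported primary tests compete. The documents do not go that far. But the cross-reference supplies the components, not a rule that an early failure stands. Even cumulative failure by 12 months leaves two tests and two treatments of dropout. The imputation and mixed-model text in 9.5 follows the repeated-measures methods and does not say how a missing 12-month composite is handled. That the log-rank is better supported makes the remedy easy, but it does not supply the missing designation.

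**Conclusion.** The point holds as an inconsistency between two stated primary outcomes, with no primary test designated in Section 9.5. The effect of choosing between tests is small if failure is irreversible and grows with the share of early failures that resolve. That share is unknown, so the 20% disagreement is conditional on the assumed 25%.

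Two stronger conclusions should be resisted. A reader might infer serious inflation of type I error, but the irreversible case adds only about one or two points to the nominal 5%. A reader might also infer that the sample size is simply wrong. It is not: 188 reproduces when failures after 12 months are counted. What the plan lacks is a censoring time, and the answer decides whether power is about 80% or about 60–65%. These power figures rest on exponential hazards and on reading the 25%, which the plan describes as loss or non-adherence, as annual loss. The 80% further assumes that the same hazard ratio holds beyond the year in which the cream is used.

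**What to change.** Before the randomization codes are broken:

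1. Rewrite 9.4.1 and 9.5 to name one primary analysis: time from surgery to first failure on any component listed in 9.1, compared by the two-sided log-rank test at 0.05. Report 12-month failure proportions as supportive, with no separate claim.
2. State whether a failure recorded at an earlier contact stands if it is absent later. No section says so, and it is a substantive decision for the sponsor.
3. State the censoring time, including how the 10–14 month window of the 12-month visit is treated.
4. Reconcile 9.2 with item 3. If follow-up is censored at the 12-month visit, restate the power at N = 188 as about 65% without loss and 60% with 25% loss (35% v 20% failure). If later failures count, say so, and reword the 12-month null hypothesis in 9.1 to match.

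Items 1 to 3 are changes of text and need no new visits or data. Item 4 is not free: censoring at 12 months means either accepting the lower power or increasing the number of women having surgery from 188 to about 266–303.
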